5.2 Study Endpoints

Primary Safety Endpoint:

Major Adverse Clinical Events (MAE) at 1 month, defined as death, target vessel revascularization (TVR), target limb amputation.

Primary Performance Endpoint:

Primary Patency at 6 month, defined as no evidence of clinically significant stenosis ($\geq 50\%$) within the stent graft or immediately above or below the treated arterial segment based on duplex ultrasound (systolic velocity ratio of >2.5), with no clinically-driven re-intervention within the stented segment.

Secondary Safety Endpoints:

- Major Adverse Events (MAE) through follow-up.
- Major adverse vascular event (MAVE) through follow-up defined as stent thrombosis, target limb amputation, clinically apparent distal embolization, defined as causing end-organ damage (e.g. lower extremity ulceration, tissue necrosis, or gangrene), procedure related arterial rupture, acute limb ischemia or bleeding event requiring transfusion.
- Major Blood Loss defined as transfusion of >2 units packed red blood cells (PRBC) through discharge.
- The combined rate of death of target vessel revascularization (TVR), index limb amputation, and an increase in Rutherford-Becker Classification by 2 classes (comparing pre- to post-procedural assessments) through follow-up.
- Deep Vein Thrombosis (DVT) on ipsilateral limb defined as a symptomatic blood clot (thrombus) in the targeted deep vein (e.g. posterior tibial) through follow-up.
- VCSS and Villalta Scale through follow-up.
- Venous Assessment (Miller Scale) through follow-up.

- Stent fracture identified via X-ray through follow-up. (Optional per standard practice. Not applicable if radiological Safety Committee approval is required e.g. BFS Germany).

Secondary Performance Endpoints:

- Technical Success defined as successful delivery of the investigational devices to the identified area and removal of delivery system.
- Procedural Success defined as successful delivery of the investigational devices to the identified area and removal of delivery system in the absence of in-hospital MAEs.
- Clinical Success defined as Limb ischemia improvement by Rutherford-Becker (improvement in scale by ≥ 1) through follow-up.
- Limb ischemia by Rutherford-Becker Classification through follow-up.
- Primary Patency through follow-up.

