5.5 Inclusion Criteria

Subjects must meet all of the following criteria to be eligible for enrollment in this trial:

- Age 18 or older.

- Willing to comply with the specified follow-up evaluation schedule.
- Women of child bearing potential must have a negative pregnancy test within 7 days prior to the index procedure.
- Severe claudication or rest pain or ischemic ulceration not exceeding ulcer of the digits of the foot (Rutherford Becker scale 3-5) with a resting ABI < 0.9. Resting TBI is utilized only if unable to reliably assess ABI. TBI must be <0.7.
- Subject is not morbidly obese (BMI<40).
- Venous Clinical Severity Score <3.
- Serum creatinine level < 2.0 mg/dL.
- BUN < 20 mg/dL.
- Patent iliac and femoral arteries/veins and access vessels, of sufficient size and morphology (including tortuosity), to allow endovascular access with 8 Fr. introducer sheath.
- Femoro-popliteal lesions ≥10 cm (TASC C and D) in length considered to be:
 - Chronic total occlusion (100% stenosis)
 - Diffuse stenosis (>50% stenosis) with moderate to heavy calcification
 - In-stent restenosis (>50% stenosis)
- Reference vessel diameter (RVD) ≥ 5.0 mm and ≤ 6.7 mm, as measured via pre-screening CTA/MRA using 3D RPR reconstruction.
- Orifice and proximal 1 cm of SFA is patent (approximately 1 cm stump).
- Patent popliteal artery 3 cm proximal to tibial plateau.
- At least 1 patent tibial artery to the foot.
- Patient has the ability to comply with the necessary follow-up examinations and tests in accordance with protocol.
- Patent femoral vein ≥ 10 mm in diameter or duplicate femoral vein.
- Subject has > 2 year life expectancy.

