9.2 Baseline Evaluation

After subjects have signed an informed consent form and before the scheduled interventional procedure, subjects will undergo a baseline evaluation. This evaluation may be conducted from an office visit within the previous 30 days. The evaluation will consist of the following:

- Subject's demographic data (sex and date of birth)
- Medical history
- Rutherford score and Ankle-Brachial Index (ABI)
- Serum pregnancy test
- Venous Clinical Severity Score
- Villalta scale
- BUN and Creatinine
- Medication history and review

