11.0 ENDPOINTS AND STATISTICAL ANALYSIS PLAN

11.1 Endpoints Analyses and Reporting of Results

The study objective is to assess the safety and performance of the PQ Bypass System to access, deliver guidewires and implant stent grafts for a percutaneous fem-pop bypass.

The study is a feasibility study with no formal hypothesis testing and therefore no required sample size. Study results will be presented using descriptive statistics. Results from this study will be used to design additional clinical studies.

All subjects will be followed on an intent-to-treat basis. The device performance will be assessed based on a per-protocol analysis of the primary safety and effectiveness endpoints. An Intent-to-treat analysis, along with other secondary analyses, will also be completed and reported.

Demographic, baseline clinical and disease characteristics, procedural results and primary, secondary and all additional endpoints will be summarized using descriptive statistics.

All statistical analyses will be performed using SAS for Windows version 9.1 or higher.

Primary Safety Endpoint Reporting:

Safety assessment is achieved by recording and measuring Major Complication rates/Serious Adverse Event rates associated with the PQ Bypass procedure. The number and percentage 6-month MAE will be presented using descriptive Statistics. Using the Score approximation, the one-sided upper 95% confidence bound will be calculated and presented.

Primary Performance Endpoint Reporting:

Descriptive statistics of the primary performance endpoint which includes total number of patent PQB grafts, number and percentage of patent PQB grafts, and the one-sided 95% CI of the percentage using the Score approximation will be presented. The lower bound of the one-sided 95% CI will be compared to the performance goal of 70% (80% historical control rate – 10% Delta.)

Secondary Endpoint Analysis:

The secondary endpoint of primary assisted and secondary patency will be summarized using Kaplan-Meier survival analysis. Life tables will be created and a Kaplan-Meier survival curve will be presented.

The secondary endpoints of Procedural Success, Clinical Success and Technical

Success will be summarized by providing point estimates, number of subjects, and 95% confidence bounds calculated using the Score approximation.

Demographic, procedural and safety data:

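### The deterioration component of the combined secondary safety endpoint needs a 2-class Rutherford-Becker rise; if the scale ends at 6, class 5 subjects cannot reach it and class 4 subjects reach it only at the top class

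*Combined protocol and SAP*

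**What the plan says.** Section 5.2 of the protocol lists, among the secondary safety endpoints, a composite that opens "The combined rate of death of target vessel revascularization (TVR), index limb amputation" and closes with "an increase in Rutherford-Becker Classification by 2 classes (comparing pre- to post-procedural assessments) through follow-up". I read the opening as death or target vessel revascularization (TVR), since the literal wording does not make sense otherwise. The Protocol Summary carries the same text.

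Entry covers only part of the scale. Section 5.5 and the Protocol Summary admit severe claudication, rest pain, or "ischemic ulceration not exceeding ulcer of the digits of the foot (Rutherford Becker scale 3-5) with a resting ABI < 0.9".

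The reference class for the change is the one taken at the baseline evaluation in Section 9.2, which lists "Rutherford score and Ankle-Brachial Index (ABI"). The same assessment is repeated at discharge (Section 9.4) and at each follow-up visit (Section 9.5).

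For improvement on the same scale, Section 5.2 sets a lower threshold: "Clinical Success defined as Limb ischemia improvement by Rutherford-Becker (improvement in scale by" at least 1). It also names Rutherford-Becker class through follow-up as a secondary performance endpoint in its own right.

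Section 19 does not define this composite, and I found no separate deterioration rule for subjects who start near the top of the scale. On analysis, Section 11.1 says "Study results will be presented using descriptive statistics".

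**The concern.** A deterioration rule based on change from baseline needs room above the baseline class. The trial deliberately enrols subjects in the upper part of the scale, then asks for a rise of 2 classes before worsening counts. If the scale has only one class above 5, a subject who enters with a digital ulcer and progresses to more extensive tissue loss is event-free on this component by construction.

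What is at stake is how the result will be read. A low or zero count of deterioration among class 5 subjects would reflect the definition and not their course, yet in a safety table it could pass for reassurance. The two directions are also treated unequally: a class 5 subject who moves to 4 is a Clinical Success, while one who moves to 6 is not a deterioration event.

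**Working it through.** The plan states no rate, power or sample size for this endpoint, so there is no figure to reproduce. The check is an enumeration.

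**Inputs**

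- Threshold: a rise of 2 classes over the pre-procedure class (Section 5.2 and Protocol Summary).
- Permitted baseline classes *b*: 3, 4, 5 (Section 5.5 and Protocol Summary).
- Reference assessment: the baseline evaluation (Section 9.2).
- Top class *T*: not printed in the documents. I assume 6 and show 5 and 7 as a range. The entry limit, "not exceeding ulcer of the digits of the foot", implies that worse tissue loss lies beyond class 5, which fits 6 better than 5.

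**Step 1: largest possible rise**

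Largest rise = *T* − *b*. With *T* = 6: 6 − 3 = 3, 6 − 4 = 2, 6 − 5 = 1. The threshold is 2, so class 5 falls short and class 4 has no slack.

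**Step 2: post-procedure classes that qualify**

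A class *c* qualifies if *b* + 2 ≤ *c* ≤ *T*.

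| Baseline class | *T* = 5 | *T* = 6 (assumed) | *T* = 7 |
|---|---|---|---|
| 3 | 5 | 5, 6 | 5, 6, 7 |
| 4 | none | 6 | 6, 7 |
| 5 | none | none | 7 |

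If the top were 5, neither class 4 nor class 5 could qualify. If it were 7, class 5 could qualify, but only at 7.

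**Step 3: exact or minimum rise**

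The table reads the threshold as 2 or more. Taken literally as exactly 2, a move from 3 to 6 (a rise of 3) would not count, and class 3 would qualify only at 5.

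**Step 4: what the definition leaves out, with *T* = 6**

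Take a rule that counts a rise of 2 or more, or any progression from baseline to the top class. Moves from 3 to 6 and from 4 to 6 are rises of 3 and 2 and already count. The rule therefore adds only moves from 5 to 6, and

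change in composite rate = (class 5 subjects who reach 6 and have no death, TVR or index limb amputation) / *N*.

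At the maximum enrolment of 100, each such subject adds 1/100 = 1 percentage point. Neither the class 5 share nor the share who worsen in this way is in the documents, so the total cannot be computed. Purely as illustration, class 5 shares of 5%, 10%, 20% and 30% (assumed) would leave 5, 10, 20 and 30 of 100 subjects unable to score on this component. Those counts cap the effect; they do not estimate it.

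**The case against.** The strongest case against the point has four parts.

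1. **The top class is outside the documents.** True. The result for class 5 depends on it, and a top of 7 would let class 5 subjects qualify. I therefore state 6 as an assumption and show the range. The wording of the entry criterion supports a class above 5.

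2. **Worsening is captured elsewhere.** Largely true. Rutherford class through follow-up is a named endpoint, and the composite still counts death, TVR and index limb amputation. The major adverse vascular event composite covers stent thrombosis, acute limb ischemia, amputation and embolization with tissue damage. Adverse events are recorded throughout (Section 12.0). A reader might infer that worsening in class 5 subjects goes unrecorded, or that they cannot meet the composite at all; the documents support neither. Still, none of these routes is certain to count a gradual move from 5 to 6 in a subject who has no amputation and no repeat procedure. Section 19 describes TVR as treatment of another lesion and defines re-intervention on the index lesion separately, which may narrow that route further.

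3. **A 2-class threshold is a legitimate choice.** Also true. That a move from 4 to 5 does not count is simply what such a threshold means, and I do not call it an error. The point concerns subjects for whom no outcome can qualify.

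4. **Changing the definition now is not clean.** Section 2.4 describes an ongoing study, which by its start date and count appears to be this one, with 60 subjects treated by May 2016 and core laboratory outcomes through 6 months for 30. Replacing a safety definition at that stage would be a post hoc change, and Section 16.3 requires ethics committee and competent authority approval for significant changes. This stands, and it is why the fix adds to the definition and does not replace it.

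**Conclusion.** The point holds, with limited weight. On the assumption that the scale ends at 6, class 5 subjects cannot score on the deterioration component and class 4 subjects can score only at the top class. Followed as written, the safety composite omits moves from 5 to 6 in a group the protocol chooses to enrol, and so can under-record worsening in the subjects with the most severe disease at entry.

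The size is unknown. Only class 5 subjects who worsen without death, TVR or index limb amputation are affected, and the baseline class mix is not given. The endpoint is secondary and descriptive, so no power, alpha or sample size changes.

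A reader might go further and call the combined rate biased downward and unfit for comparison between sites or with other series. The documents do not support that. They name no other target quantity against which the rate would be biased, and they plan no cross-site or external comparison of this endpoint; the only performance goal concerns patency. What can be said is that the deterioration count should be read with the baseline class mix beside it.

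**What to change.** In the Protocol Summary and Section 5.2:

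- Keep the present composite and clarify its last component as a rise of 2 or more classes from the pre-procedure class.
- Add a second version of the composite whose last component is a rise of 2 or more classes, or any progression from baseline to the top class. State what the top class is.
- Tabulate the deterioration component by baseline class (3, 4, 5), with the number of subjects in each, and show any rise of 1 or more class alongside.
- Label the second version as added after enrolment began, and report both versions.

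No new visit, test or subject is needed, because Rutherford class is already collected at baseline, discharge and every follow-up visit. The cost is a few extra table rows, a protocol amendment with its approvals, and a reported rate that may be slightly higher under the added version.

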8.0 STUDY PROCEDURE

8.1 Vascular Access and Guidewire Delivery

Investigators will access the target lesion and the corresponding ipsilateral vein using standard percutaneous techniques and devices. Patient eligibility will be confirmed prior to insertion of the study device, based on procedural imaging and sheath placement.

After eligibility confirmation, the Venous Locator (VL), Percutaneous Anastomotic Device (PAD) and Balloon Dilator (BD) will be used to deliver a guidewire from the arterial segment proximal to the target lesion, through the femoral vein and back into the reconstituted artery distal to the target lesion. This procedure is described in detail in the Guidewire Delivery System and Balloon Dilator IFUs (**Appendix II**). The number of deployment attempts for guidewire placement access at each anastomosis will be recorded.

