- **Non-device or procedure related death** – Death NOT related to any procedure (index or subsequent) intended to treat the target vessel or death not related to the Study Device.

Deep Vein Thrombosis (DVT) on Ipsilateral Limb

A blood clot (thrombus) in the targeted deep vein (e.g. posterior tibial). A deep vein thrombosis is symptomatic. A deep vein thrombosis is distinct from the presence of mild fibrin/thrombus with no hemodynamic impact or the intentional I occupancy of the vein by the graft or asymptomatic occlusive thrombus (see **Venous Classification** below)

Device Deficiency

Inadequacy of the Study Device with respect to its identity, quality, durability, reliability, safety or performance. Device deficiencies include malfunctions, use errors, and inadequate labeling.

Device Time

Number of minutes from initial Study Device insertion to final Study Device removal. It does not include time needed to perform adjunctive procedures.

Explant

Removal of the Study Device implant for any reason.

Fluoroscopy Time

Total fluoroscopy time (minutes) used during the index procedure and includes time utilized for adjunctive procedures performed during the index procedure.

Intensive Care Unit Time

See post-procedure ICU time

Life Expectancy > 2 Year

The duration of time the test subject is expected survive post procedure. Subjects must not have a concurrent medical condition that would cause expected survival to be less than 2 years.

Malignant Tumor¹

A tumor that invades surrounding tissues, is usually capable of producing metastases, may recur after attempted removal, and is likely to cause death of the host unless adequately treated.

Major Adverse Event (MAE)

¹ <http://www.medilexicon.com>

Composite endpoint of death, target vessel revascularization (TVR) or any amputation of the index limb. See individual events for detailed definitions.

Major Adverse Vascular Event (MAVE)

Composite endpoint of stent thrombosis, target limb amputation, clinically apparent distal embolization, defined as causing end-organ damage (e.g. lower extremity ulceration, tissue necrosis, or gangrene), procedure related arterial rupture, acute limb ischemia or bleeding event requiring transfusion.

Myocardial Infarction (MI)²

Typical chest pain and either a Q-wave or non Q-wave MI as described below. Myocardial infarction is a component of MAE.

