The need for mechanical ventilation beyond the first 24 hours post-index procedure (and/or re-intervention) or the need for re-intubation or ventilator support after the first 24 hours (unless the subject was ventilator dependent pre-procedure).

Secondary intervention

Any visit to the operating room or catheterization laboratory subsequent to the PQ Bypass procedure to treat an adverse event related to the disease, the index procedure or the study device.

Secondary Patency

revascularization of occlusion (100%) within the stent graft or immediately above or below the treated arterial segment with less than 50% residual stenosis

Serious Adverse Event (SAE)

Any undesirable event occurring which led, could have led or might lead either directly or indirectly to the death or serious deterioration in the health of a subject, user or another person, regardless of whether the event was caused by the medical device.

Stroke or Transient Ischemic Attack (TIA)

- **Stroke** - A new neurological deficit lasting more than 24 hours, or lasting 24 hours or less with a brain imaging study showing infarction.
- **TIA** - A neurological deficit lasting less than 24 hours and, if an imaging study is performed, shows no evidence of infarction. These events may occur anytime throughout a subject's study participation and may or may not require intervention.

Stent Graft Occlusion

Complete blockage of blood flow through the Stent Graft as determined by traditional imaging (e.g. DUS, CTA, MRA or Angiography).

Stent Graft Placement Accuracy

Estimated distance (mm) from the operator's intended target as compared to the actual position placed as assessed via angiography during the index procedure.

Target Lesion Revascularization (TLR)

A re-intervention on the index lesion site.

Target Vessel Revascularization (TVR)

Treatment of another lesion at the target vessel site.

Technical Success

Successful delivery of the investigational devices to the identified area and removal of delivery system.

Unanticipated Adverse Device Effect (UADE)

An adverse device effect which by its nature, incidence, severity or outcome has not been identified in the risk analysis report.

Vascular Access Type

Method of entry into the vascular system. Categorized as either surgical cut down or percutaneous.

Venous Classification (Miller Scale)

A means of classifying observations in the deep vein in which the stent graft is implanted:

- 0: Patent, no presence of fibrin or thrombus

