- 1: Patent, thin film fibrin sheath
- 2: Patent, presence of mild fibrin/thrombus without hemodynamic impact
 - a) located in gutter adjacent to anastomosis
 - b) located in body of graft
- 3: Intentional occupation of vein with no anticipated flow
- 4: Asymptomatic Occlusive thrombosis

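### The DVT endpoint depends on an undefined targeted vein and the Miller Scale lacks a grade for flow-limiting non-occlusive thrombus, so some ipsilateral deep-vein clot enters neither endpoint

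*Combined protocol and SAP*

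**What the plan says.** Section 5.2 and the Protocol Summary list as a secondary safety endpoint: "Deep Vein Thrombosis (DVT) on ipsilateral limb defined as a symptomatic blood clot (thrombus) in the targeted deep vein (e.g. posterior tibial) through follow-up". Section 19.0 repeats both conditions, site and symptoms: "A blood clot (thrombus) in the targeted deep vein (e.g. posterior tibial). A deep vein thrombosis is symptomatic". The same entry then marks out what is not DVT: "A deep vein thrombosis is distinct from the presence of mild fibrin/thrombus with no hemodynamic impact". It also sets apart planned occupation of the vein by the graft and silent occlusive thrombus, and refers the reader to the venous classification.

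That classification, the Miller Scale, is a secondary safety endpoint in its own right. Its scope is "A means of classifying observations in the deep vein in which the stent graft is implanted". Grade 0 is a clear vein, grade 1 a thin fibrin film, and grade 3 planned occupation with no flow expected. The two grades that describe thrombus are "2: Patent, presence of mild fibrin/thrombus without hemodynamic impact" and "4: Asymptomatic Occlusive thrombosis".

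Section 8.1 takes the guidewire from the artery above the lesion "through the femoral vein and back into the reconstituted artery distal to the target lesion". The stent grafts are then placed to complete the bypass (Section 8.2), and eligibility depends on the femoral vein (Section 5.5). Venous duplex is done at discharge and at every follow-up visit (Sections 9.4 and 9.5). Section 11.1 summarises secondary endpoints descriptively.

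**The concern.** The endpoint's label and its rule do not match. The label promises the limb. The rule counts one vein, does not say which, and illustrates it with a calf vein although the device occupies the femoral vein. Two sites or two readers could classify the same popliteal clot differently, and both could defend their reading from the text.

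The companion scale does not close the gap. Section 19.0 uses effect on flow to separate trivial thrombus from DVT. Yet in the graft-bearing vein, thrombus on the worse side of that line has no category if it is silent and not occlusive.

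Venous safety distinguishes this procedure from an intra-arterial stent graft, and Section 7.1 names venous flow disruption, including DVT, as a risk of the Stent Graft System. Neither the MAE nor the MAVE composite contains a deep-vein event, so DVT and the Miller Scale are the only endpoints that classify venous thrombus. Section 11.1 says that the results will be used to design further studies, so an ambiguous definition would carry over into them.

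**Working it through.** The plan states no DVT rate, threshold or venous sample size, so there is no figure to reproduce. The check is whether the two definitions together cover every kind of thrombus.

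Inputs:
- DVT rule (Sections 5.2 and 19.0): symptomatic, and in the targeted deep vein.
- Miller scope (Section 19.0): the graft-bearing vein only.
- Miller thrombus grades: 2 (mild, no effect on flow) and 4 (occlusive, asymptomatic).
- Assumption: the graft-bearing femoral vein is a targeted vein. Under the narrow reading it is the only one. Under the wide reading, suggested by the posterior tibial example and the limb label, other ipsilateral deep veins count too.

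| Thrombus | Symptoms | Graft-bearing vein | Other ipsilateral vein, narrow | Other ipsilateral vein, wide |
|---|---|---|---|---|
| Non-occlusive, no effect on flow | yes | DVT or Miller 2 | neither | DVT |
| Non-occlusive, no effect on flow | no | Miller 2 | neither | neither |
| Non-occlusive, affects flow | yes | DVT | neither | DVT |
| Non-occlusive, affects flow | no | **neither** | neither | neither |
| Occlusive | yes | DVT | neither | DVT |
| Occlusive | no | Miller 4 | neither | neither |

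Cells that fall in neither endpoint:
- Graft-bearing vein: 1 of 6.
- Other ipsilateral deep veins, narrow reading: 6 of 6. Total 1 + 6 = 7 of 12.
- Other ipsilateral deep veins, wide reading: 3 of 6. Total 1 + 3 = 4 of 12.

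The first row has its own ambiguity. Section 5.2 would count a symptomatic mild clot as DVT, while Section 19.0 sets mild thrombus without effect on flow apart from DVT. In the graft-bearing vein this does not matter, because Miller 2 picks it up. Elsewhere, under the wide reading, applying the Section 19.0 carve-out would move one more cell to neither, giving 5 of 12.

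These counts show where the definitions leave gaps. The cells are not equally likely, so the counts do not estimate a proportion of events. If all 100 planned subjects were evaluable, each unclassified subject would be 1/100 = 1 percentage point. The documents do not say how many such subjects to expect.

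**The case against.** The strongest reply is that the two endpoints were designed to complement each other. Section 19.0 draws the line openly: symptomatic clot is DVT, and silent findings go to the venous classification. On that view the word asymptomatic in grade 4 is deliberate. This stands. A reader might infer that the worst veins, those with symptomatic occlusion, are lost. They are not, because they meet the DVT definition; what is missing is only a pointer from the Miller table to them.

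A second reply is that venous harm is recorded elsewhere. VCSS and Villalta are secondary safety endpoints, all adverse events are recorded (Section 12.0), and the DSMB reviews adverse events (Section 14.4). This also stands, so a general statement that the trial under-counts venous harm would go too far. But VCSS and Villalta are severity scores and do not count clots, and no tabulation of venous thrombus from adverse events is specified.

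Third, the posterior tibial example may mean that the targeted vein was intended broadly. If so, symptomatic popliteal clot is counted. The documents therefore do not establish that it is excluded; they leave the matter open.

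Fourth, one might object that grade 3, a planned state, sits between two thrombus grades. No ordinal analysis of the scale is planned, and Section 11.1 summarises categorical variables by counts and percentages, so this is not an error in the analysis.

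Finally, limiting DVT to symptomatic events is a stated, pre-specified choice. That is fair, and the symptomatic rate should stay. The choice does not explain the undefined vein or the missing category.

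**Conclusion.** The point holds in a limited form. Followed as written, silent, flow-limiting, non-occlusive thrombus in the graft-bearing vein has no place in either venous-thrombus endpoint. The same is true of silent clot in other ipsilateral deep veins and, on the literal reading, of symptomatic clot there. The term for the targeted vein is undefined, and its example does not fit the femoral route in Section 8.1. The DVT rate taken alone will therefore understate venous thrombosis if such findings occur, and it should at least be read together with Miller grade 4.

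The size of the effect cannot be estimated, because the documents report no DVT or Miller results. A percentage-point shortfall could be given only by assuming both the true thrombosis rate and the share left out, and nothing in the documents anchors either. The conclusion assumes that the graft-bearing vein is a targeted vein. It concerns descriptive secondary endpoints and does not touch the primary endpoints, alpha, power or sample size. It is an inexpensive improvement to the plan.

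**What to change.** 1. Reconcile the DVT entries in Sections 5.2 and 19.0 with the route in Section 8.1 and the Miller scope in Section 19.0. Define the targeted deep vein so that the endpoint matches its ipsilateral-limb label, and say whether a symptomatic mild clot without effect on flow is DVT.
2. Keep the symptomatic DVT rate. Beside it, report any new thrombus in any ipsilateral deep vein within the field of the scheduled venous duplex, leaving out intended graft occupancy and splitting symptomatic from asymptomatic. New thrombus is identifiable because a history of DVT is an exclusion (Section 5.6) and a pre-procedural venous ultrasound is taken (Section 9.1).
3. Add a Miller category for non-occlusive thrombus that affects flow, and a cross-reference line for symptomatic thrombosis, so that every graft-bearing vein is accounted for in the table.

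The cost is edits to definitions, case report forms and reading forms, using scans already scheduled. The venous figure may look less favourable. Section 2.4 reports 60 subjects treated by May 2016, so earlier reads would need re-classification to avoid mixed definitions. Section 8.3 describes a lower-extremity duplex and does not show that the iliac veins are covered, so the new line should be limited to the field actually scanned.
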